9.2 Other Medical Device or Medication Specified for Use During the Study

During the clinical study, additional medical devices and/or medications that are required in conjunction with the treatment include the following:

- CLEAR CARE[®] Cleaning & Disinfecting Solution supplied by sponsor to be provided to subjects for use during the study.
- Lubrication/rewetting drops will not be permitted.

9.3 Treatment Assignment / Randomization

Subjects will be randomized in a 1:1 manner to receive treatment (lens) in crossover sequence: test product then comparator product or comparator product then test product, respectively.

Sequence	EDC/randomization integration system	Lens Name
Sequence 1	LID022821/AOHP	Alcon serafilcon A/AOHP
Sequence 2	AOHP/LID022821	AOHP/Alcon serafilcon A

Only after signing the ICF, a subject will be assigned a subject number by the electronic data capture system.

A randomization list will be generated using a validated system that automates the random assignment of treatment (lens sequence) to randomization numbers in the specified ratio. Subjects will be assigned treatment (lens sequence) according to the randomization list uploaded in the randomization system. The randomization list will be generated and maintained by the study sponsor

At Visit 1 after completion of BCVA (OD, OS, logMAR distance with manifest refraction), biomicroscopy, and fitting of investigational products (trial assessments for test and comparator) all eligible subjects will be randomized via the EDC/randomization integration system to one of the treatments (lens sequences). The investigator or delegate will access the respective system after confirming that the subject meets all the eligibility criteria. A randomization number will be automatically assigned to the subject according to the subject randomization list but will not be communicated to the site user. The EDC/randomization integration integration system will inform the site user of the treatment (lens sequence) assignment to be dispensed to the subject.

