3 PROTOCOL SUMMARY

Investigational	Device
product type	
F	
Study type	Interventional
	$T \rightarrow D \rightarrow A \rightarrow A$
Investigational	Test Product: Alcon serafilcon A contact lenses (LID022821)
products	Comparator Product: ACUVUE [®] OASYS with HYDRACLEAR [®]
	PLUS Technology contact lenses
Purpose and	The purpose of this study is to assess the clinical performance of the
Scientific	investigational Alcon serafilcon A contact lenses as compared to
Rationale for	marketed ACUVUE [®] OASYS with HYDRACLEAR [®] PLUS
the Study	Technology contact lenses when worn on a daily wear modality.
	The design of this study is
	justified based upon preclinical and clinical testing, as described within
	the investigator's brochure. AOHP contact lenses were chosen as the
	comparator product because these lenses also are reusable contact lenses
	(see Package Insert for AOHP contact lenses). Subjects will be provided
	with CLEARCARE [®] Cleaning & Disinfecting Solution to use with the
	study lenses.
	-

Brief	This study aims to compare the clinical performance
Summary of	at the end of the
the Protocol	replacement cycles of Alcon serafilcon A contact lenses compared to ACUVUE [®] OASYS with HYDRACLEAR [®] PLUS Technology contact lenses, when worn on a daily wear modality. Volunteer subjects aged 18 or over who are habitual spherical soft contact lens wearers (excluding current/previous AOHP habitual lens wearers and daily disposable lens wearers), have at least 3 months of contact lens wearing experience, and who wear their habitual lenses at least 5 days per week and at least 8 hours per day, will be included. This is a prospective, randomized, double-masked, bilateral, crossover study. The expected outcome of this study is to demonstrate noninferiority in the visual acuity at distance when wearing Alcon serafilcon A contact lenses compared to AOHP contact lenses
Objective(s)	 The primary objective of this study is to demonstrate noninferiority in the visual acuity at distance when wearing Alcon serafilcon A contact lenses compared to ACUVUE[®] OASYS with HYDRACLEAR[®] PLUS Technology contact lenses when worn on a daily wear modality.
	• The safety objective is to describe the safety profile of the study products.
Endpoint(s)	Primary EfficacyDistance visual acuity (logMAR) with study lenses at Week 1

	Safety
	• Adverse events
	Biomicroscopy findings
	Device deficiencies
Assessment(s	B) Effectiveness
	• BCVA (logMAR distance with manifest refraction)

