7.3 Rationale for Duration of Treatment/Follow-Up

Subjects will wear each study product bilaterally for their respective wear cycles on a daily wear modality.

. The lenses will be provided by a qualified unmasked study staff member in such a manner that the subject and the investigator remain masked to the lens type.

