9.4 Treatment masking

This study is double masked with subjects randomized to use Alcon serafilcon A and AOHP for the duration of the two 2-week treatment periods.

In the event of a medical emergency where the knowledge of subject treatment is required, an individual investigator will have the ability to unmask the treatment assignment for a specific subject after contacting an appropriate study sponsor representative if time allows.

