9.5 Accountability Procedures

Upon receipt of the IPs, the investigator or delegate must conduct an inventory. During the study, designated unmasked study staff must provide the IPs to the subjects in accordance with their randomization assignment. Throughout the study, the investigator or delegate must maintain records of IP dispensation and collection for each subject. This record must be made available to the study monitor for the purposes of verifying the accounting of IP supplies. Any discrepancies and/or deficiencies between the observed disposition and the written account must be recorded along with an explanation. All IPs sent to the investigator must be accounted for by study sponsor personnel, and in no case be used in an unauthorized situation.

The investigator should make every effort to collect unused lenses, foils, and supplies from subjects.

It is the investigator's responsibility to ensure that:

- All study products are accounted for and not used in any unauthorized manner
- All unused products are available for return to the study sponsor, as directed

• Any study lenses or solutions associated with a device deficiency or with any productrelated adverse event (i.e., ADE or SADE) are returned to the study sponsor for investigation, unless otherwise directed by the sponsor. Refer to Section 11 of this protocol for additional information on the reporting of device deficiencies and AEs and the return of study products associated with these events.

The investigator is responsible for proper disposition of all unused IPs at the conclusion of the study, according to the instructions provided in the MOP.

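### Do sections 9.3 and 9.5 unmask the investigator by naming the investigator or a delegate for randomization access and dispensing records?

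*Protocol*

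**What the plan says.** Several sections of the protocol bear on who may know the lens sequence.

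- **7.3** has a qualified unmasked staff member provide the lenses "in such a manner that the subject and the investigator remain masked to the lens type".
- **9.3** describes the randomization step at Visit 1: "The investigator or delegate will access the respective system after confirming that the subject meets all the eligibility criteria". The randomization number is withheld, but the "system will inform the site user of the treatment (lens sequence) assignment to be dispensed to the subject". The labels in the system column of the 9.3 table are LID022821/AOHP and AOHP/LID022821. The Protocol Summary ties LID022821 to the test lens, and the abbreviation list defines AOHP as the marketed comparator.
- **9.4** opens with "This study is double masked with subjects randomized to use Alcon serafilcon A and AOHP". For a medical emergency, with the prior contact expected only when there is time for it, the section adds that "an individual investigator will have the ability to unmask the treatment assignment for a specific subject after contacting an appropriate study sponsor representative".
- **9.5** says that "designated unmasked study staff must provide the IPs to the subjects in accordance with their randomization assignment". The next sentence says that "the investigator or delegate must maintain records of IP dispensation and collection for each subject". Later in 9.5 the investigator is asked to try to recover unused lenses and foils.
- **11.5** says masked information is not to be disclosed during the study, requires the sponsor to be told of every code break, and refers to 9.4 for who is masked and who is not.

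**The concern.** A site could follow the sentence in 9.3 to the letter, have the investigator log in, and show that person the sequence. In a two-period crossover one view reveals the lens in both periods. This would bypass the controls in 9.4 and 11.5: it would not be an emergency, the sponsor would not be contacted, and no code break would be reported. The per-subject records in 9.5 offer a second way to the same information, and in that paragraph the unmasked role is attached to dispensing but not to the records.

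The investigator makes three judgements that are assigned by name and could be influenced: whether a change is clinically relevant and so reported as an adverse event (11.2), and the intensity and causality of each event (11.3). If the same person also measured visual acuity with the study lenses, knowledge of the lens could reach the primary noninferiority comparison.

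**Working it through.** No arithmetic applies. The protocol states no figure that depends on this point, and no sample size, margin or confidence level enters it. The check is whether the sections can all be followed at once and, if so, what they require.

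**Step 1. Who could operate the system or keep the records?** The wording allows three cases.

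| Person who sees the sequence | 9.3 and 9.5 as worded | 7.3 (investigator masked) | 11.5 (no disclosure of masked information) |
|---|---|---|---|
| Investigator | allowed | breached | breached |
| Delegate who is meant to be masked | allowed | investigator still masked | breached |
| Delegate from the unmasked staff | allowed | met | met |

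Only the third case satisfies all the sections. The general phrase in 9.3 and 9.5 offers a choice, and the specific rules elsewhere settle it. The sections differ in precision, but they do not contradict each other.

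**Step 2. Does the unmasked role exist?** Yes. 7.3 and 9.5 both rely on it for dispensing. The site user in 9.3 is told what is to be dispensed, so the natural reader of that screen is the dispenser, whom the protocol already defines as unmasked.

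**Step 3. Are readable labels a fault?** No. Both of the two labels name both products, but someone at the site must know which lens to hand over. The comparator comes in commercial foil (Table 9–2), and the test foil carries the material name and identifier (Table 9–1). A neutral code on the screen would hide nothing from the person holding the lenses.

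**Step 4. Should 9.3 carry the emergency controls?** No. 9.4 and 11.5 govern breaking the code for someone who is masked. Routine assignment to an unmasked dispenser breaks no code.

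**Step 5. Where could an effect arise if a site got it wrong?**

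- Visit 1 BCVA, biomicroscopy and fitting, and the eligibility check, all come before randomization in 9.3, so they are untouched.
- Visual acuity with study lenses and follow-up biomicroscopy would be affected only if the person who saw the sequence performs them. The visible text does not say who does, and 10.2 provides for delegation.
- The three adverse event judgements could be affected. Under 12.6 the safety analysis is descriptive, with no inferential testing, and under 11.3 the sponsor makes its own causality assessment and may upgrade seriousness or causality.

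**Step 6. What of the foils?** The sentence in 9.5 on recovering unused lenses and foils names the investigator without a delegate. Collection of study product is also listed as a study procedure in 10.2.3, and 10.2 has the investigator delegate procedures to qualified personnel. It can therefore go to the unmasked staff under the same reading.

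**The case for a change.** The best case for a change is that masking should not depend on inference at about 14 sites. 9.3 names the investigator first and does not say the delegate must be unmasked. 9.5 uses the unmasked role in one sentence and drops it in the next. The foil sentence names only the investigator. If a role list in 9.4 does restrict access, the wording of 9.3 and 9.5 is looser than that list and should match it. The repair would be a few words plus a system permission, using staff the protocol already requires.

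The textual part of this stands: the wording is looser than 7.3, and writing that the delegate is unmasked, or cross-referring to 9.4, would be tidier. The inference that masking is at risk does not stand. It requires a site to apply 9.3 or 9.5 while disregarding 7.3 and 11.5, and it treats the role list cited by 11.5 as absent when it was probably redacted from the public copy. System permissions and detailed site procedures belong to operational set-up and the Manual of Procedures, which is not at hand.

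**Conclusion.** The concern does not hold as a reason to change the plan. Two per-subject steps (system access in 9.3, dispensation and collection records in 9.5) are worded more loosely than 7.3, and one sentence on recovering foils names the investigator alone. A trial run to all sections stays masked, because only an unmasked delegate satisfies them together. No size or direction of bias can be derived from the document, and no route to the Week 1 visual acuity comparison is shown. What could be touched by a site's error is three adverse event judgements feeding a descriptive safety analysis.

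The conclusion assumes that sites read 9.3 and 9.5 together with 7.3 and 11.5. It does not depend on what the unseen list in 9.4 says, provided that list does not give masked persons access to the sequence. This is a gap in wording that a competent site fills correctly; clarifying it is optional.

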9.4 Treatment masking

This study is double masked with subjects randomized to use Alcon serafilcon A and AOHP for the duration of the two 2-week treatment periods.

In the event of a medical emergency where the knowledge of subject treatment is required, an individual investigator will have the ability to unmask the treatment assignment for a specific subject after contacting an appropriate study sponsor representative if time allows.

9.5 Accountability Procedures

Upon receipt of the IPs, the investigator or delegate must conduct an inventory. During the study, designated unmasked study staff must provide the IPs to the subjects in accordance with their randomization assignment. Throughout the study, the investigator or delegate must maintain records of IP dispensation and collection for each subject. This record must be made available to the study monitor for the purposes of verifying the accounting of IP supplies. Any discrepancies and/or deficiencies between the observed disposition and the written account must be recorded along with an explanation. All IPs sent to the investigator must be accounted for by study sponsor personnel, and in no case be used in an unauthorized situation.

The investigator should make every effort to collect unused lenses, foils, and supplies from subjects.

It is the investigator's responsibility to ensure that:

- All study products are accounted for and not used in any unauthorized manner
- All unused products are available for return to the study sponsor, as directed

• Any study lenses or solutions associated with a device deficiency or with any productrelated adverse event (i.e., ADE or SADE) are returned to the study sponsor for investigation, unless otherwise directed by the sponsor. Refer to Section 11 of this protocol for additional information on the reporting of device deficiencies and AEs and the return of study products associated with these events.

The investigator is responsible for proper disposition of all unused IPs at the conclusion of the study, according to the instructions provided in the MOP.

9.6 Changes to concomitant medications, treatments/ procedures

After the subject is enrolled into the study, the investigator must instruct the subject to notify the study site about:

- Any new medications
- Alterations in dose or dose schedules for current medications,
- Any medical procedure or hospitalization that occurred or is planned
- Any nondrug therapies (including physical therapy and blood transfusions).

The investigator must document this information in the subject's case history source documents.

10 STUDY PROCEDURES AND ASSESSMENTS

Subjects will be expected to attend 7 office visits, as shown below.

Visit #	Visit Type	Visit Window
Visit 1	Screening/Baseline	N/A
Visit 2	Dispense Lens 1	2 (at least 48 hours) - 4
		days after Visit 1 (Washout
		period with habitual spectacles
		only after Visit 1)
Visit 3	Week 1 Follow-up Lens 1	7 -0/+ 1 days after Visit 2
Visit 4	Week 2 Follow- up Lens 1	7 -0/+ 1 days after Visit 3

Visit 5	Dispense Lens 2	2 (at least 48 hours) - 4 days after Visit 4 (Washout period with habitual spectacles only after Visit 4)
Visit 6	Week 1 Follow-up Lens 2	7 -0/+ 1 days after Visit 5
Visit 7	Week 2 Follow-up Lens 2/Exit	7 -0/+ 1 days after Visit 6

Unscheduled Visits and Early Exit Visits are allowed, if necessary.

Study lenses will be provided to the subjects to take home for daily wear during the course of the trial.

Study randomization will occur at Visit 1 to determine assigned lens sequence. Subjects will be provided the assigned lenses to take home at Visit 2, Visit 3, Visit 5 and Visit 6. Study contact lens fitting will occur at Visit 1 for both study lenses. If a subject cannot be successfully fit (either study lens) according to the study lens fitting guides as determined by the investigator, they will be required to exit from the study.

Lubrication/rewetting drops will not be permitted during this study.

10.1 Informed Consent and Screening

The investigator or delegate must explain the purpose and nature of the study, and have the subject read, sign, and date the IRB/IEC-approved informed consent document. The subject must sign the ICF before any study-specific procedures or assessments can be performed, including study-specific screening procedures. Additionally, have the individual obtaining consent from the subject and a witness, if applicable, sign and date the informed consent document.

The investigator or delegate must provide a copy of the signed document to the subject and place the original signed document in the subject's chart, or provide documentation as required by local regulations.

10.2 Description of Study Procedures and Assessments

Study-specific procedures and assessments described here may include standard of care; other standard of care procedures performed in the clinical management of the subject are not excluded.

Detailed descriptions of assessments and procedures are provided in the MOP. The investigator is responsible for ensuring responsibilities for all procedures and assessments are delegated to appropriately qualified site personnel.

10.2.1 Demographics

Obtain demographic information including age, race, ethnicity, and sex.

10.2.2 Medical History

Collect medical history information, including information on all medications used within the past 30 days. Include herbal therapies, vitamins, and all over-the-counter as well as prescription medications. Throughout the subject's participation, obtain information on any changes in medical health and/or the use of concomitant medications.

Medical History and Concomitant Medications will be collected in the eCRF as outlined in the MOP

10.2.3 Investigational Product Compliance

Review subject compliance with the IP usage and adjunct product usage and collect all used and unused study IPs and other products that were dispensed.

10.2.4 Adverse Event Collection: Safety Assessment

Assess and record any adverse events that are observed or reported since the previous visit, including those associated with changes in concomitant medication dosing in the subject source documents. See Section 11 for further details regarding AE collection and reporting.

10.2.5 Slit Lamp Biomicroscopy: Safety Assessment

SLE of the cornea, iris/anterior chamber and lens must be performed in both eyes before instillation of any diagnostic eye drops.

10.2.6 Device Deficiencies: Safety Assessment

Assess and record any device deficiencies that are reported or observed since the previous visit. Requirements for reporting device deficiencies in the study can be found in Section 11.

10.2.7 Best Corrected Visual Acuity: Safety Assessment

LogMAR visual acuity testing for both eyes must be performed prior to any assessment requiring administration of eye drops to dilate the eyes, or any assessment requiring contact with the eye.

10.3 Unscheduled Visits

If a subject visit occurs between any regularly scheduled visit and the visit is conducted by study personnel, this visit must be documented as an unscheduled visit. If the subject seeks medical attention outside the clinic (for example, at an emergency room) or at the clinic but is seen by non-study personnel, the investigator is to capture adverse event-related information on the Adverse Event form upon becoming aware.

During all unscheduled visits, the investigator must conduct the following procedures:

- Collect adverse event information
- Collect Device Deficiency information
- Record changes in medical condition or concomitant medication
- Biomicroscopy
- Review lens wear calendar

The investigator may perform additional procedures for proper diagnosis and treatment of the subject. The investigator must document this information in the subject's case history source documents.

If during an unscheduled visit the subject is discontinuing the IP or discontinuing from the study, the investigator must conduct Exit procedures according to Table 3-1 Schedule of Study Procedures and Assessments and Section 10.4.3, as possible.

10.4 Discontinued Subjects

10.4.1 Screen Failures

Subjects who were excluded from the study after signing the informed consent and prior to randomization to IP.

The investigator must document the reason for screen failure in the subject's case history source documents.

Subject numbers must not be reused.

10.4.2 Discontinuations

Discontinued subjects are individuals who voluntarily withdraw or are withdrawn from the study by the investigator after signing the informed consent, including screen failures.

Subject numbers of discontinued subjects must not be reused (i.e., subject replacement is not allowed).

Subjects may discontinue from study or study treatment at any time for any reason. Subjects may also be discontinued from study treatment at any time if, in the opinion of the investigator, continued treatment poses a risk to their health.

For subjects discontinuing from the study, the investigator must complete all Exit procedures according to Table 3-1 Schedule of Study Procedures and Assessments and Section 10.4.3, if the subject is willing and able, and if in the opinion of the investigator it is safe for the subject to do so.

The investigator must document the reason for study or treatment discontinuation in the subject's case history source documents.

To ensure the safety of all subjects who discontinue early, investigators must assess each subject and, if necessary, advise them of any therapies and/or medical procedures that may be needed to maintain their health.

10.4.3 Schedule of Procedures and Assessments for Subjects Discontinued from Investigational Product

Other than screen failures, if a subject discontinues from the study, the subject should undergo an Early Exit Visit. Refer to Table 3-1 and the MOP for details.

